**Table 5: Challenges and Solutions**

	Potential Challenge	Solution
1	Participant recruitment	Research registries, community partnerships, snowball, and social media
2	Participant retention/dropout	Data collection timepoints, incentives, at least bi-weekly phone calls/text messages/emails
3	Non-adherence	Manipulation checks
4	Access to Wi-Fi enabled device	Wi-Fi enabled device provided, if needed
5	Access to Wi-Fi	Access to Wi-Fi provided, if needed, then resources for free/reduced Wi-Fi
6	Scheduling difficulty	Flexibility, multiple offerings, use of Doodle polling
7	Health or safety concerns	Health resources, notification of IRB and relevant authority as needed
8	Death of a care recipient	Pair transition plan (bereavement support and other resources offered)

## J. Internal Validity

Threats to internal and external validity exist. For example, the study team will not be able to control additional external support that the current caregiver is receiving simultaneously that may impact study findings. The team will also not be able to control if the relationship between the peers is not conducive to peer support. However, participants will be instructed to contact the research team should any issues arise. In the conduct of pre- and post- tests are strategically timed based on prior studies with a goal to help avoid any desire of the participants to remain consistent in their responses. Data collection forms will be completed via telephone or video call (via Zoom®) with a research team member for consistency and to avoid missing data. Study participants may have participated in the prior FamCare Study. This relationship over the time with the PI and the study may impact their perception of the study. However, the benefits of their continued participation in this co-created community-based study outweighs this threat and will be acknowledged in the study results. Over the course of the study, participants may drop out. To mitigate this, the research team will maintain constant connection with them through frequent check-ins via phone call, text messages, and email for check-ins and data collection as outlined.

To ensure threats to internal and external validity in the qualitative portion of the study, several measures will be taken to help to ensure trustworthiness of findings. At least three independent coders to help to ensure validation of conclusions. Member checking with up to two participants in each category (current and former caregivers) will be conducted to verify if understanding of data rang true to them. Study team interview training will help to ensure regularity in the delivery process. All interviewers will also be trained in interview data collection procedures for consistency in this process to reduce variability of findings as a result. Data will be reported with sufficient descriptive data with the intent to ensure that data transferability is possible to applicable settings or groups.

For this pilot study, that is thus not fully powered, data obtained regarding feasibility and acceptability of the intervention will not be generalizable to the larger population. Therefore, data obtained will be used to inform the next step study to test effectiveness of the intervention.

## K. Data Analysis

Descriptive statistics will be conducted on all participant demographic data using SPSS® or similar software.

Aim 1: Feasibility and acceptability of the Pair 2 Care Intervention in current ( $n=15$ ) and trained former ( $n=15$ ) African American ADRD family caregivers will be determined by our eligibility criteria, recruitment, and retention data (e.g., consent, drop out, refusal rates), protocol adherence, satisfaction, and appropriateness of the intervention for broader dissemination. We will conduct descriptive statistics for this Aim using proportion for categorical measures (recruitment, retention, and protocol adherence) and mean±standard deviation for continuous measures (80% satisfaction and 80% appropriateness). Interviews will be conducted with current caregivers to gather in-depth data on their Pair 2 Care Intervention experiences, including feedback on the likelihood of the intervention meeting the needs of African American ADRD caregivers. Interviews will be analyzed as described below. Aim 2: Descriptive statistics will be used to summarize sample characteristics and outcome measures (anxiety, depression, quality of life, social support, self-efficacy for surrogate decision making, and intent to use palliative care/hospice services) at each time point. For each outcome, we will use mixed-effects linear modeling for repeated measures to model the outcome as a linear function of fixed-effect of time. The model will also include subject-specific random intercepts to adjust for within-subject clustering from repeated measures. We hypothesize that at 6 months as compared to baseline, current caregivers will report less anxiety and depression, higher quality of life, higher social support, higher self-efficacy for surrogate decision making, and higher intent to use palliative care/hospice services. From the mixed-effects modeling, we will test this hypothesis by deriving contrast estimate of change of outcome between baseline and 6 months.

Power analysis suggested that our sample size ( $n=15$ ) will have only 38% power to detect a medium effect size of Cohen's  $d = 0.5$  for outcome change from baseline at 6 months. This effect size is equivalent to a clinical meaningful difference. Therefore, we will not rely on statistical significance. Instead, results interpretation will be guide by point estimates, precision of the estimates (e.g., 95% confidence interval), effect sizes, and their clinical significance.

Qualitative Data Analysis: Caregiver interview recordings will be transcribed, verified for accuracy, and combined with field notes for analysis. Data analyses will be ongoing and iterative to inform additional probes and analyses. Content analysis will be completed via Dedoose software©,39 using qualitative descriptive methods to describe themes that emerge. Independent coding will be done by three team members for triangulation. Coders will discuss and reconcile coding

for consensus. Member checking with up to two participants will be conducted to verify understanding of data.

Transcribed interviews, field notes, and graphic recording will all be considered as part of study data analysis. Data analyses will be conducted as data are collected to determine when data saturation is achieved. Therefore, data analyses will be iterative. All strategies mentioned in the Internal Validity Section of this protocol will continue as described to ensure trustworthiness of data in the analyses process. Content analysis will be conducted using qualitative descriptive methods to describe themes that emerge from these data. Qualitative data analysis by members of the research team as well as using traditional word processing and paper and pencil methods. Dedoose®39 software supports analysis of implicit “deeper” themes that are not necessarily explicitly identified by the coders based on their thematic coding. Independent coding will be conducted by three members of the research team for triangulation of data. The coders will meet to discuss and reconcile coding to 100% agreement. Member checking with up to two participants in each category (family caregivers, healthcare providers, and community stakeholders) will be conducted to verify if understanding of data rang true to them. Qualitative and quantitative data will be initially analyzed separately then brought together brought together for side-by-side comparisons. Both types of data will be compared and related to provide further explanation of study findings. A plain language summary of the results of the research (prepared at a 4th grade reading level). Study findings will be disseminated via scholarly conference paper and poster presentations as well as local community-based newsletters to ensure a vast and varied readership.

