perceived benefits of peer support while caregiving and their willingness to serve as peer mentors to current family caregivers. Additional data from healthcare provider and community stakeholders support the need and potential benefits of peer support for ADRD caregivers. Based on these preliminary findings, there is an urgent need and exciting opportunity to address the unmet palliative care needs of current caregivers through peer support. For this innovative study, we will use the experiential expertise of former family caregivers as mentors to help current family caregivers as mentees with advance care planning and healthcare decision making. The purpose of this study is to test a peer support intervention for family caregivers who are caring for a loved one living with dementia. Peer Support for Caregivers of African Americans Living with Dementia (Pair 2 Care) is a co-created culturally sensitive caregiver peer support intervention. The following specific aims will be addressed:

[figure not shown]
**Aim 1:** Conduct feasibility and acceptability testing of Pair 2 Care in current ( $n=15$ ) and trained former ( $n=15$ ) African American ADRD family caregiver peers paired based on congruent identity traits (e.g., relationship to care recipient, gender identity, etc.). We will determine if Pair 2 Care is feasible and acceptable by evaluating eligibility criteria, recruitment and retention data, protocol adherence, satisfaction, and feedback on appropriateness of the intervention for broader dissemination.

**Aim 2:** Assess preliminary intervention outcomes of caregiver anxiety, depression, quality of life, social support, self-efficacy for surrogate decision making, and intent to use palliative care or hospice services to determine potential effectiveness of the Pair 2 Care Intervention. At 6 months as compared to baseline, current caregivers (mentees) will report less anxiety and depression, higher quality of life, perceived social support, and self-efficacy for surrogate decision making as well as intent to use palliative care or hospice services as part of advance care planning and healthcare decision making.

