### **III. Procedures**

#### **Overall Procedures**

All study procedures will be approved by The Ohio State University (OSU) Institutional Review Board (IRB). Procedures will be conducted remotely allowing flexibility for participation. Intervention development initially began using stakeholder data collected from our FamCare Study as previously described. A total of 15 people who are currently caring for a loved one (current caregivers) and total of 15 people who cared for a loved one who lived with dementia (former caregivers) will be enrolled in the Pair 2 Care research study. Mentors may be assigned an additional mentee. Former caregivers (mentors) will complete up to two 1-hour training sessions to become mentors to current caregivers (mentees). Former caregivers will be called mentors and current caregivers will be called mentees. Each mentor and mentee will be paired for 6 months for peer support. We will attempt to select mentors and mentees for pairing based on something they have in common as identified using the (see Participant Intake Form). During the Pair 2 Care program/intervention, mentors will provide non-judgmental, flexible, culturally sensitive support to their mentees and share their personal caregiving experiences. This may include information such as the following: accessing/selecting healthcare providers, attending doctor visits, attending worship services, coronavirus pandemic/endemic, exercise, faith, family dynamics, finances, healthcare decision making, mental health, nutrition, physical health, sleep, social activities, spirituality. Data collected during the participant screening process such as family caregiver type, etc., may be used from consented individuals. Once each week during the 6 months connection, mentees will be sent a short survey (see Appendix for Weekly Mentee Interaction Assessment Response Form) by text, email, and/or phone call to complete about their interaction with their mentor during the last week. If not completed by the mentee, a text email

and/or phone call reminder will be sent within a couple days after as a reminder to complete it. A weekly text/email/reminder phone call message may be used to: 1) thank participants for being in the study, 2) remind mentees and mentors to connect, and or 3) remind mentees to complete their Weekly Mentee Interaction Assessment Response Form.

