## B. Sample and Setting

A sample of  $n=15$  current family caregivers (mentees) and  $n=15$  former family caregivers (mentors) who self-identify as being Black/African American caregiver of an older adult living with or who lived with ADRD will be recruited to pilot test the Pair 2 Care program/intervention. For this short duration study, participants will be recruited from the Central Ohio area – Columbus area and surrounding communities. As requested by our prior study participants for this co-created intervention, this study is being conducted virtually. While recruitment may occur via phone, video call, email, or in-person using the IRB-approved study flier and recruitment scripts, consenting and data collection will be completed remotely. Therefore, participants (mentors and mentees) are not required to meet in-person for this study.

[figure not shown]

```
graph TD; A[Ongoing CAB A] --> B[6-month caregiver intervention]; B --> C[1-month follow-up]
```

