**Measurement / Instrumentation:** Demographic data (e.g., age, gender, caregiving relationship) will be collected from all caregivers using the respective mentor and mentee demographic form (see appendix). State anxiety (Spielberger State Anxiety Inventory - STAI-S), depression (Center for Epidemiological Studies – Depression - CES-D), quality-of-life (Caregiver-Targeted Quality of Life – CGQOL), self-efficacy for surrogate decision making (Surrogate Decision Making Self-Efficacy Scale - SDM-SES), social support (Medical Outcomes Study Social Support Survey – MOS SSS), and intent to use palliative care/hospice (Mentee Palliative and Hospice Care Intent Form) data will be collected from mentees. Care recipient dementia stage (Quick Dementia Rating System - QDRS) and behavioral and psychological ADRD symptoms (Neuropsychiatric Inventory Questionnaire - NPI-Q) data will also be collected (see Table 3) (see appendix). Audio-recorded interviews (using the Mentee or Mentor Interview Guide – see appendices) conducted at one-month follow up via Zoom®, phone, or other virtual format with participants will characterize their experiences. Mentors will have the option to complete the interview at Month 6 or 7. Mentees will complete the interview at Month 7 (1 Month follow-up). Interviews will be conducted with participants to gather in-depth data on their Pair 2 Care Intervention experiences, including feedback on the likelihood of the intervention meeting the needs of African American ADRD caregivers. A member of the research team will connect with

former caregivers at the 3- and 6-month timeframe for feedback on how the mentoring process is going.

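### Aim 2's 6-month contrast: the intent form appears not to be collected at Month 6, and for the other outcomes time coding and the role of Month 7 are left open

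*Combined protocol and SAP*

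**What the plan says.** Section III.K applies one model to all six Aim 2 outcomes: anxiety, depression, quality of life, social support, decision-making self-efficacy and palliative/hospice intent. The fixed part is to "model the outcome as a linear function of fixed-effect of time". The random part is a mentee-level intercept: "The model will also include subject-specific random intercepts to adjust for within-subject clustering from repeated measures". The hypothesis, which names intent among the six, is tested by "deriving contrast estimate of change of outcome between baseline and 6 months". The section does not say whether time is continuous or a visit factor, or which visits enter. It names no covariance beyond the random intercept.

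On timing, the Overall Procedures state that "Each mentor and mentee will be paired for 6 months for peer support", and the flow chart in section III.B shows a "6-month caregiver intervention" followed by a 1-month follow-up. Section III.H has mentees surveyed at the start, at 3 and 6 months, and at that follow-up. Section III.G dates the follow-up: "Mentees will complete the interview at Month 7 (1 Month follow-up"). The visits are therefore at 0, 3, 6 and 7 months, and the last falls after support has ended.

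Table 3, as extracted, lists the intent form for mentees at baseline and in the last column, which also holds the mentee interview. It does not appear in the column for 3 and 6 months. The last column's heading did not survive extraction.

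On use, Aim 2 in section II assesses these outcomes "to determine potential effectiveness of the Pair 2 Care Intervention". Section III.K sets statistical significance aside: "results interpretation will be guide by point estimates, precision of the estimates (e.g., 95% confidence interval"), effect sizes and clinical significance.

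**The concern.** Because significance is set aside, the 6-month contrast and its interval are in effect the Aim 2 result, and they will inform the next study. For intent, the hypothesised 6-month change seems to have no 6-month measurement behind it. For the other five outcomes, two analysts following section III.K could fit different models. Under one of them, an estimate labelled 6 months would depend more on the post-support visit than on the 6-month visit. If the choice is left until the data are in, it can be made with the estimates in view.

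**Working it through.** **The plan's own figure.** Section III.K states 38% power for d = 0.5 with n = 15. A two-sided 5% paired t-test gives 43.8%. About 38% results with, for example, 13 completers (38.2%) or d on the score SD with correlation 0.4 (37.7%). The test, alpha, correlation and drop-out behind the figure are not stated, so it is not shown to be wrong. Nothing below depends on it.

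**Inputs.** Visits at 0, 3, 6 and 7 months (sections III.G and III.H); 15 mentees; random intercept (section III.K). Trajectories and correlations are assumptions, with outcome SD set to 1.

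**1. Intent, observed at 0 and 7 only.**
- With a visit factor there is no Month 6 level, so Month 6 minus baseline cannot be estimated.
- With linear time the mean month is 3.5, the deviations are -3.5 and +3.5, and their sum of squares is 24.5. The contrast is 6 × slope, with weights ±6 × 3.5/24.5 = ±6/7. It is 6/7 of the Month 7 change, with no Month 6 information in it.

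**2. Other outcomes, linear time, four visits.** The mean month is 16/4 = 4. The deviations are -4, -1, 2 and 3, and their sum of squares is 16 + 1 + 4 + 9 = 30. Multiplying each deviation by 6/30 gives

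6-month contrast = -0.8·M0 - 0.2·M3 + 0.4·M6 + 0.6·M7.

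The Month 7 to Month 6 weight ratio is 0.6/0.4 = 1.5. With complete data and nominal months it is the same at any within-mentee correlation. If only 0, 3 and 6 months enter, the weights are -1, 0, 1, which is exactly Month 6 minus baseline. A visit factor also gives M6 - M0.

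**3. Size, for a true 6-month change of 0.50 SD.**

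| Assumed course (months 0, 3, 6, 7) | Linear time, four visits |
|---|---|
| Linear to Month 7 (0, 0.25, 0.50, 0.583) | -0.05 + 0.20 + 0.35 = 0.50 |
| Linear gain, held (0, 0.25, 0.50, 0.50) | -0.05 + 0.20 + 0.30 = 0.45 |
| Plateau by Month 3 (0, 0.50, 0.50, 0.50) | -0.10 + 0.20 + 0.30 = 0.40 |
| Linear gain, half lost at Month 7 (0, 0.25, 0.50, 0.25) | -0.05 + 0.20 + 0.15 = 0.30 |
| Linear gain, all lost at Month 7 (0, 0.25, 0.50, 0) | -0.05 + 0.20 + 0 = 0.15 |

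The visit factor returns 0.50 in every row.

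**4. Precision, assuming equal correlation 0.6.** The squared weights sum to 0.64 + 0.04 + 0.16 + 0.36 = 1.2 for linear time and 1 + 1 = 2 for the visit factor.
- SE, linear time: √(1.2 × 0.4/15) = 0.179.
- SE, visit factor: √(2 × 0.4/15) = 0.231.
- Ratio: 0.231/0.179 = 1.29. Half-widths are about 0.36 and 0.46.
- RMSE of linear time: √(0.05² + 0.179²) = 0.19 if a linear gain is held and √(0.10² + 0.179²) = 0.20 with the plateau, against 0.23 for the visit factor.
- Break-even bias: √(0.231² - 0.179²) = 0.146 SD.

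**5. Covariance (secondary).** With complete data, the random-intercept variance for M6 - M0 is in effect the average of the six pairwise difference variances. Suppose correlation decays exponentially to 0.6 at 6 months. The differences at lags 3, 6, 7, 3, 4 and 1 months then have variances 0.451, 0.800, 0.898, 0.451, 0.577 and 0.163, which average 0.557. The true value at lag 6 is 0.800, so the model SE is √(0.557/0.800) = 0.83 of what it should be. Simulated 95% coverage for the visit factor is about 90%, against about 95% for a paired interval. With milder mixtures of stable, decaying and noise components it is 93–94%. With extra variance at Month 7 the interval errs the other way, covering 97–99%.

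**The case against.** The strongest reply is that the time-coding harm needs two things the plan does not say: continuous time, and Month 7 in the model. Deriving a contrast fits a visit factor naturally, and Month 6 against baseline is already the stated target. If gains are held, the bias is 0.05–0.10 SD against a half-width of about 0.36, and linear time has the smaller RMSE. This is an acknowledged pilot, and the outcome summaries planned for each visit would show any gap between Months 6 and 7. All of this stands, and it makes the second part a request to state the choice. The summaries would not, however, change the modelled contrast.

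The 1.5 ratio is also less fixed than it looks. Section III.G allows a 2-week window. If actual dates enter, shifting Months 6 and 7 by one week in opposite directions gives ratios from 1.22 to 1.86. Drop-out to 10 or 11 of 15 changes it little (1.46–1.49).

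A reader might infer that the random-intercept interval is correct only when all visits share one variance and one correlation. That is too strong. With complete data it is enough that all pairwise visit differences have equal variance. With visit variances 0.6, 1.0, 1.4 and 0.8 and correlations of 0.43–0.68, simulated coverage was still 94.9%. Nor would a paired interval reveal a failure reliably. Even under equal correlation 0.6, its width relative to the model's runs from 0.77 to 1.31 (5th to 95th percentile).

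On intent, the objection is that the schedule is read from a damaged table. That is fair and calls for a check of the source. The column's contents still identify it, since sections III.G and III.H both place the mentee interview at the 1-month follow-up.

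**Conclusion.** The concern holds in three parts of unequal weight.

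- **Intent** carries the point. Subject to confirming Table 3, the hypothesised 6-month change has no Month 6 measurement. No time coding can supply one, and a straight line only rescales the Month 7 change by 6/7.
- **The other five outcomes** have a real ambiguity with a conditional effect. Under continuous time with four visits, complete data and nominal months, the post-support visit outweighs Month 6. An assumed 0.50 SD change is then estimated as 0.45 or 0.40 if gains are held, and as low as 0.15 if they vanish by Month 7. With complete data the bias is absent if time is a visit factor or Month 7 is left out.
- **The covariance assumption** is secondary. The interval can be too narrow if correlation falls with time, but the documents give no correlations.

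A reader might conclude that the planned analysis is biased, or that linear time is always the worse choice. The documents support neither: they do not fix the coding, and linear time is more precise while its bias stays below about 0.15 SD.

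**What to change.** 1. **Intent.** Check Table 3 in the source. If there is no Month 6 form, either report and label this outcome as the Month 0-to-7 change, or add the form at Month 6. Cost: a change of label, or one extra form for each mentee.
2. **Section III.K, other outcomes.** State that time is a visit factor with levels 0, 3, 6 and 7 months, that the planned contrast is Month 6 minus baseline, and that Month 7 versus Month 6 is a separate contrast. Cost: a few sentences, and an interval about 29% wider than with linear time. If gains are held, this also gives up the smaller RMSE of linear time. Make the choice before outcome data are seen.
3. **Optional.** Report a paired interval for the 0-to-6-month change beside the model, as one that does not need the equal-difference-variance assumption. It should not be presented as a test of that assumption or as the main estimate, because it uses only mentees with Month 6 data. With 10–11 of 15 retained at random, and under the same assumed correlation of 0.6, its half-width is about 0.59–0.62, against 0.52–0.54 for the visit-factor model.

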The Recruitment Script (see appendix) will be used for phone, video call, email, or in-person recruitment along with the study flier (see appendix). Community-based organizations such as nursing homes, churches, and dementia-focused organizations may share study fliers with potential participants such as through email via listservs, posting on their organization social media sites, or posting study fliers within their organizations using the Community Partner Recruitment (via email, phone, video call, or in-person) along with the study flier. The FamCare Lab Website will have a page dedicated to the Pair 2 Care Study that will include the study flier, Study Introduction Note, and the Study Welcome Video (see script in appendix). The Study Welcome Video will also be placed on the lab website's home page. Potential participants or community partners may choose to share the study flier with others in their contacts, and they may post the flier on their social media sites e.g., Facebook®, Twitter®, and Instagram®. Additionally, the PI and study team members may give caregiving presentations in the community as requested, attend health fairs, such as at nursing homes or other community-based organizations that may include sharing the study flier and offering continuing education credits as needed. These community presentations are educational presentations that the PI conducts as part of her citizenship in the local community based on her expertise. These presentations are given regularly on topics such as palliative and end-of-life care, family caregiving, and dementia, etc. as requested by community-based organizations. Following such community engagements, the IRB-approved study flier may be made available to attendees as with distribution at local health fairs. There will be no additional study information included in the presentations. Snowball methods will also be used for recruitment of study participants. Potential participants will contact the research team either in-person, via phone call, or email for additional study information, and eligibility screening. This convenience sampling approach will be augmented with snowball recruitment methods to identify additional potentially eligible caregiver study participants. Additionally, enrolled participants will also be asked if they know of anyone else who may qualify to participate in the study. If so, the participant will either pass along the study information and PI contact information and potential participant themselves will contact the PI if interested to facilitate snowball recruitment methods. Otherwise, if the participant agrees to reach out to other potential caregiver(s) to ask if it is okay to share their contact information with the study team, the PI or a member of the research team will contact the potential participant to provide study information and determine eligibility using the Caregiver Recruitment Script followed by the Caregiver Screening Form (see appendix).

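### Mentors may be shared, but the Aim 2 model has no mentor level: if mentees of one mentor change alike, the 95% intervals are somewhat too narrow

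*Combined protocol and SAP*

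**What the plan says.** Overall Procedures allows sharing: "Mentors may be assigned an additional mentee". The same sentence recurs in section G, under the pairing of mentors and mentees. The planned numbers are 15 mentees and 15 mentors (Overall Procedures; section B), so sharing is an option and not the base design. The documents do not say how many mentors may be shared.

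For Aim 2, section K will "model the outcome as a linear function of fixed-effect of time". On the random part it says: "The model will also include subject-specific random intercepts to adjust for within-subject clustering from repeated measures". The quantity of interest comes from "deriving contrast estimate of change of outcome between baseline and 6 months". There is no mentor or pair term, no cluster-robust variance and no sensitivity analysis for a shared mentor. Section K sets significance aside and reads the results through point estimates, their precision (with the 95% interval as the example), effect sizes and clinical significance.

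**The concern.** The mentor is the person who delivers the intervention, and section G leaves the timing, length, content and medium of contact flexible. Section J accepts that the team cannot control how well a pairing works. Differences between mentors would therefore arise after baseline and could act on change, which is what Aim 2 estimates. Two mentees with the same mentor may then carry less independent information than two mentees with different mentors.

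A random intercept per mentee accounts for repeated visits by the same person but not for similarity between people. If such similarity exists, the standard error of the mean change is too small. Because the plan relies on intervals rather than tests, their width is part of the reported result. Section J also says the data will inform the next study.

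**Working it through.** **Plan's own figure.** The plan gives no interval width. The nearest figure is power: the sample "will have only 38% power to detect a medium effect size of" d = 0.5. A two-sided paired t-test with n = 15 (df = 14, noncentrality 0.5 × √15 = 1.94) gives 43.8%, so 38% is not reproduced. Inputs that the plan does not state can produce it; 13 mentees, for example, gives 38.2%. The test, alpha, sidedness and attrition are not given, so this is a separate matter and not proof of an error. It is not used below.

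**Inputs.** From the documents: 15 mentees, and one additional mentee per mentor, read as at most two. Assumed: a correlation ρ of change within mentor of 0.05 to 0.30, s shared mentors, and no missing data. With s shared, there are 15 − s mentors. The maximum is s = 7 (7 × 2 + 1 = 15, so 8 mentors).

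**Formulas.**
- Variance inflation of the mean change: D = 1 + ρ × 2s/15.
- Width factor from correlation alone: √D.
- Width factor with mentor-level degrees of freedom: √D × t(mentors − 1)/t(14), where t is the 97.5% point. t(14) = 2.145, t(13) = 2.160, t(10) = 2.228 and t(7) = 2.365.

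| Shared | Mentors | D (ρ = 0.05; 0.30) | √D | t ratio | Total |
|---|---|---|---|---|---|
| 0 | 15 | 1; 1 | 1; 1 | 1 | 1; 1 |
| 1 | 14 | 1.007; 1.040 | 1.003; 1.020 | 1.007 | 1.011; 1.027 |
| 4 | 11 | 1.027; 1.160 | 1.013; 1.077 | 1.039 | 1.053; 1.119 |
| 7 | 8 | 1.047; 1.280 | 1.023; 1.131 | 1.103 | 1.128; 1.247 |

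The t ratio applies even at ρ = 0. It is the price of estimating the variance from fewer units and does not measure how far the planned interval is wrong.

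**On the effect-size scale.** The half-width for a mean change with n = 15 is 2.145/√15 = 0.554 SD of change. One shared mentor at ρ = 0.30 makes it 0.554 × 1.020 = 0.565. Seven make it 0.554 × 1.131 = 0.627, or 0.554 × 1.247 = 0.691 with mentor-level degrees of freedom.

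**Coverage of the planned model.** This was simulated with 15 mentees, three visits, time as categories and 40,000 runs per scenario.
- Mentor effect on change, 0.10 of change variance: 94.6% with 0 or 1 shared, 94.0% with 3 and 93.5% with 7.
- Mentor effect on change, 0.30 of change variance: 93.7% with 0 shared, 93.2% with 1, 92.2% with 3 and 90.0% with 7. The shortfall at 0 shared comes from the random-intercept-only structure when change varies between mentees. That is separate from sharing.
- Mentor effect on level only, equal at all visits: 94.9% to 95.3%, even with 7 shared, because it cancels from the change.

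**Sharing on its own.** For the simple mean-change interval at ρ = 0.30, coverage ignoring mentor is about 93.3% with 4 shared and 91.7% with 7. A mentor-clustered interval on mentors − 1 degrees of freedom gives about 94.5%.

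**The case against.** The strongest reply is that the problem may never arise and would be small if it did. One-to-one pairing is possible with 15 and 15. The 14-, 11- and 8-mentor rows are illustrations, not forecasts. It is tempting to derive them from the Table 4 benchmarks (90% of mentors trained, 70% retained), but the retention benchmark covers both groups. Section I says that a remaining peer may continue and may be analysed separately; it does not mention reassignment. With 1 shared mentor, correlation alone adds at most about 0.01 SD to the half-width (0.565 − 0.554). No numeric decision rule depends on an interval bound, since Table 4 concerns feasibility and acceptability only. All of this stands, and it limits the importance of the point.

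It is also fair that a few shared mentors cannot support a well-estimated mentor variance. That argues for a sensitivity interval beside the planned one. It does not argue for leaving the shared mentors unreported.

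A reader might also worry about two relatives of one care recipient enrolling, because "enrolled participants will also be asked if they know of anyone else who may qualify to participate in the study". The eligibility criteria do not rule this out, but nothing shows that it will happen and no size can be given, so it is not part of this point.

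**Conclusion.** The point holds conditionally. The documents allow shared mentors, and the only Aim 2 model has no place for them. The intervals are too narrow if sharing occurs and changes are positively correlated within mentor. For ρ of 0.05 to 0.30, the shortfall from correlation alone is 0.3–2% with 1 shared mentor, 1–8% with 4 and 2–13% with 7. With mentor-level degrees of freedom the totals are 1–3%, 5–12% and 13–25%. The values of ρ and s are assumptions, as is the limit of two mentees per mentor.

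Two stronger readings are not supported:
- *The intervals are too narrow whenever a mentor is shared.* They are not if ρ is zero or negative, or if the mentor effect is on level only.
- *The effective sample is closer to the number of mentors than to 15.* With 7 shared mentors, 15/D runs from 14.3 to 11.7, always nearer 15 than 8. With 4 shared it runs from 14.6 to 12.9, passing the midpoint of 13 only when ρ exceeds about 0.28.

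**What to change.** Record every mentor assignment for each mentee, with mentor ID and dates, so that any later reassignment is visible. Report how many mentors were shared. If any were, add to section K a 95% interval for the baseline-to-6-month change clustered by mentor, using a small-sample-corrected cluster-robust variance with mentor-level degrees of freedom. Present it at least as a sensitivity analysis beside the planned interval. State in advance how a mentee with more than one mentor is placed in a cluster.

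Adding only a mentor random intercept would not do this, because it cancels from a within-mentee change.

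The cost is an ID variable with dates and a short addition to section K. When mentors are shared, the added interval will be slightly wider and somewhat noisier. When pairing stays one-to-one, it equals the ordinary mean-change interval.
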